## Attribution of the AE:

- Definite The AE is clearly related to the study treatment.
- Probable The AE *is likely related* to the study treatment.
- Possible The AE *may be related* to the study treatment.
- Unlikely The AE is doubtfully related to the study treatment.
- Unrelated The AE *is clearly NOT related* to the study treatment.

As stated above, attribution and expectedness for adverse events will not be evaluated with respect to uproleselan alone; these evaluations will be done based on the combination of uproleselan and the above commercial agents as a single study treatment.

## 7.3 Adverse Event Collection

All Grade 3 and higher non-hematologic adverse events occurring through transplant day +30 (regardless of attribution or expectedness) will be routinely reported. Routine reporting is accomplished via the Adverse Event (AE) Case Report Form (CRF) within the study database. Adverse events that require collection are defined in Tables 5 and Table 6 and must be reported in routine study data submissions on the toxicity case report forms. This includes adverse events previously reported in an expedited manner (see section 7.5).

Table 5. Hematologic Adverse Event Routine Collection Requirements					
Grade 1-4	Short-term, reversible grades 1-4 hematologic laboratory abnormalities are				
	expected during transplant and do not require collection or reporting.				
Grade 5	All grade 5 AEs should be collected and reported.				

Table 6. Non-Hematologic Adverse Event Routine Collection Requirements				
Grade 1	Grade 1 AEs do not need to be collected unless they otherwise meet criteria			
	for a serious adverse events (SAE) as described in Section 7.4.			
Grade 2	Unexpected grade 2 AEs will be collected with the following exceptions:			
	• Abnormal laboratory values or test results that are not associated with			
	clinical signs or symptoms and are not considered clinically significant			
	(i.e., require no treatment or further diagnostic testing)			
Grade 3	All grade 3 non-hematologic AEs should be collected and reported.			
Grade 4	All grade 4 non-hematologic AEs should be collected and reported.			
Grade 5	All grade 5 non-hematologic AEs should be collected and reported.			

Between Day +30 - Day +100 the following adverse events should be collected and reported to the Sponsor:

- Events that are deemed to be Serious and Unexpected
- The following adverse events of special interest would be deemed SAEs: VOD/SOS; graft failure; graft rejection; and > or = grade 3 pulmonary toxicity per CTCAE criteria.

These events should be reported to the Sponsor Investigator within 5 business days of discovery.

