#### **10.3** Other Post-Transplant Evaluations

10.3.1 Mucosal barrier injury-associated laboratory-confirmed bloodstream infection (MBI-LCBI)

MBI-LCBI will be assessed from day 0 through Day +30 and defined according to CDC criteria: https://www.cdc.gov/nhsn/pdfs/pscmanual/4psc\_clabscurrent.pdf\*-

Oral mucositis severity will be assessed daily from Day 0 through Day +14, using CTCAE v5 criteria.

Intestinal mucositis severity will be assessed daily from Day 0 through Day +14, using

CTCAE v5 criteria for enterocolitis.

10.3.2 Hepatic veno-occlusive disease (VOD)/sinusoidal obstruction syndrome (SOS) will be will be diagnosed and graded according to the pediatric (<18 years) and adult (≥18 years) European Society for Blood and Marrow Transplantation (EBMT) criteria (Appendix C).

All reported cases of sinusoidal obstruction syndrome will be adjudicated (diagnosis and grading) by a physician with expertise in this area.

- 10.3.3 Acute GVHD will be assessed through 1 year according to the Blood and Marrow Transplant Clinical Trials Network Manual of Procedures. https://web.emmes.com/study/bmt2/public/MOP/BMTCTNTechnicalMOPv3.pdf
- 10.3.4 Physical exam and performance status collected at least on Day 0, +30, +100, +365, and +730. May be collected more often as per institutional guidelines.
- 10.3.5 Chronic GVHD will be assessed through 1 year using the NIH consensus criteria.
- 10.3.6 Relapse will be assessed per institutional guidelines through 2 years post transplant.

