## 13.6 Analysis of Primary Endpoints

To address primary objective in section 1.3 Phase 1, the RP2D will be identified through the application of the 3+3 design. Accrual will be temporarily suspended after the enrollment of each cohort of 3 patients on a dose level, until all 3 patients have either completed the DLT observation period (30 days) or experienced a DLT.

To address primary objective in section 1.3 Phase 2, all observed toxicities will be summarized

using frequencies, proportions, and 95% confidence intervals by type (organ affected or laboratory determination), severity (by CTCAEv5.0), attribution, and expectedness. Only the maximum grade for each type of toxicity will be tabulated for each patient.

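### Section 13.6 promises toxicity proportions with 95% CIs at every grade, but section 7.3 does not collect most grade 1, expected grade 2 and transient hematologic events

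*Protocol*

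**What the plan says.** **Analysis.** Section 1.3 makes description of safety at the RP2D the Phase 2 primary objective. For it, section 13.6 has all observed toxicities summarized "using frequencies, proportions, and 95% confidence intervals by type (organ affected or laboratory determination), severity (by CTCAEv5.0), attribution, and expectedness". Each patient counts once per toxicity type, at the maximum grade. No grade floor is set and hematologic events are not excluded.

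**Collection.** Section 7.3 decides what reaches the adverse event form:

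- Non-hematologic, grade 3 and above: "All Grade 3 and higher non-hematologic adverse events occurring through transplant day +30 (regardless of attribution or expectedness) will be routinely reported".
- Non-hematologic, grade 2 (Table 6): "Unexpected grade 2 AEs will be collected with the following exceptions". The exceptions are laboratory or test results without clinical significance.
- Non-hematologic, grade 1 (Table 6): "Grade 1 AEs do not need to be collected unless they otherwise meet criteria" for a serious adverse event.
- Hematologic, grades 1-4 (Table 5): "Short-term, reversible grades 1-4 hematologic laboratory abnormalities are" (the sentence continues) "expected during transplant and do not require collection or reporting".
- Grade 5: collected in all cases.

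Events already sent by the expedited route of section 7.5 are also entered, so serious events of any grade reach the form.

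**Expectedness.** Section 7.2 treats everything listed in sections 7.1.1 to 7.1.8 or the consent documents as expected. Section 7.1.2 extends this to any other toxicity known to occur with this type of transplant.

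**A conflicting instruction.** Section 7.2 also asks investigators for the characteristics of every adverse event from enrollment until the participant goes off study, with none of the limits in 7.3.

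**The concern.** Severity and expectedness are both dimensions of the 13.6 summary and filters on the data behind it. Because 7.1.2 leaves the expected category open-ended, most grade 2 events in a busulfan-based transplant will fall in it. A patient whose worst event of a given type is an expected, non-serious grade 2 has no routine record of that type, and the maximum-grade rule then counts that patient as free of it.

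The resulting proportion is low because of the collection rule, and its confidence interval describes sampling error around the wrong quantity. Someone comparing these rates with the adult data in section 2.1, or planning the full-scale trial of section 2.4, could take a shortfall in collection for good tolerability.

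Two features make the gap uneven as well as large. The wording in Tables 5 and 6 is permissive: events need not be collected, but they are not barred. And 7.2 can be read as asking for all of them. Sites may therefore submit different data, leaving some cells partly filled with no clear denominator.

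**Working it through.** **1. The plan's own figure.** Section 13.3 gives an exact 95% interval width of 0.379 for an observed proportion of 0.20 with 20 patients. The Clopper-Pearson interval for 4/20 is 0.0573 to 0.4366, width 0.3793. The figure reproduces, so the same method and n = 20 are used below.

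**2. Collection set against analysis.**

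| Category | Collected under 7.3 | Can 13.6 estimate a rate? |
|---|---|---|
| Grade 3-5 non-hematologic, through Day +30 | All | Yes |
| Grade 5, any type | All | Yes |
| Grade 2 non-hematologic, unexpected | Yes, less non-significant laboratory results | Only this subset, not the grade 2 total |
| Grade 2 non-hematologic, expected | Only if serious | No |
| Grade 1 non-hematologic | Only if serious | No |
| Grade 1-4 hematologic laboratory, short-term and reversible | Not required | No |
| Grade 1-4 hematologic, prolonged | No row in Table 5; short-term is not defined | Depends on site judgment |

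**3. What an uncollected category yields.** If no events of a category are recorded among 20 patients, the exact upper 95% limit is 1 - 0.025^(1/20) = 0.168. The interval 0 to 16.8% excludes every true rate above 16.8%.

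**4. Partial collection.** Let p be the true grade 2 rate for a toxicity and e the share of those events that are expected and non-serious, hence not collected. Both are assumptions; the protocol gives neither. The recorded count is X ~ Binomial(20, p(1 - e)). Coverage is the probability that the exact interval computed from X contains p.

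Worked case, p = 0.30 and e = 0.5, so the recorded rate is 0.15:

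- The upper limit is 0.2487 for 1/20 and 0.3170 for 2/20, so the interval reaches 0.30 only if X is at least 2.
- Coverage = 1 - 0.85^20 - 20 × 0.15 × 0.85^19 = 1 - 0.0388 - 0.1368 = 0.824. Counts so high that the lower limit exceeds 0.30 have negligible probability.

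The same calculation over a range:

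| True rate p | e = 0.5 | e = 0.8 | e = 0.9 | e = 1.0 |
|---|---|---|---|---|
| 0.20 | 0.878 | 0.558 | 0.332 | 0 |
| 0.30 | 0.824 | 0.340 | 0.120 | 0 |
| 0.50 | 0.383 | 0.011 | 0.000 | 0 |

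All fall short of 0.95, and coverage worsens as the toxicity becomes more common or more of its events count as expected.

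**5. What does not depend on these cells.** DLT is the formal Phase 2 endpoint (13.2.1). The study calendar has RRT evaluated daily for inpatients, or three times weekly for outpatients, through Day +30. The TRM rule uses deaths and the RRT rule uses the Table 4 toxicities. Oral and intestinal mucositis are graded separately ("Oral mucositis severity will be assessed daily from Day 0 through Day +14, using CTCAE v5 criteria", with a matching rule for enterocolitis) and analyzed by severity in 13.7. Neutrophil and platelet engraftment are endpoints of their own.

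**The case against.** The strongest reply is that 13.6 speaks of observed toxicities, which can be read as those that 7.3 brings in, and that table layouts and footnotes belong in a statistical analysis plan. Abridged collection is also sensible in a transplant trial, where low-grade events and transient cytopenias are nearly universal; Table 5 says as much. No stopping or dose decision rests on these cells.

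Most of this stands. Abridged collection is not the error. But reading observed as collected does not repair 13.6: it would still attach intervals to grade- and expectedness-specific proportions whose numerators are cut by rule. The analysis is stated in the protocol, so this is not a detail left for later.

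Three stronger readings are tempting, and the documents do not support them:

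- **That the report will print 0/20 with an interval for uncollected cells.** The protocol nowhere says that such cells will be filled with zeros. The 0 to 16.8% interval shows what would follow if they were.
- **That the report will contradict itself on mucositis.** If 12 of 20 patients had grade 2 oral mucositis as their worst grade (assumed), one could imagine 60% (36% to 81%) in the 13.7 analysis and 0% (0 to 17%) under 13.6. That requires 13.6 to draw only on the adverse event form, which it does not say. The daily CTCAE grades are observed toxicities too.
- **That all hematologic and low-grade events are lost.** Table 5 exempts only short-term, reversible laboratory abnormalities, and serious events of any grade still enter through 7.5.

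**Conclusion.** The mismatch between 13.6 and 7.3 is real but confined to the descriptive low-grade and hematologic rates. Taken from the data as collected, grade 1 proportions, grade 2 proportions that include expected events, and proportions for transient grade 1-4 hematologic abnormalities would be understated, and their 95% intervals would fall short of nominal coverage. At n = 20 and an assumed true rate of 30%, coverage drops from 0.82 when half the events are uncollected to 0.34 when 80% are, and to zero when all are. These figures rest on assumed rates and shares and on 20 patients at the RP2D. For a toxicity rarer than 16.8%, even an interval from 0/20 would still include the true value, though the point estimate would be too low.

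A reader might infer that the trial's safety conclusion is compromised. It is not: the DLT proportion, the TRM and RRT rules and the grade 3-5 non-hematologic rates through Day +30 do not use the abridged data. The point should be corrected before analysis, but it does not threaten the design.

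**What to change.** In section 13.6:

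- Limit proportions and 95% intervals to grade 3-5 non-hematologic toxicity through Day +30 and to all grade 5 events.
- Take all-grade oral and gastrointestinal mucositis from the daily assessments in 10.3.1.
- List other collected grade 1-2 and hematologic events without rates.
- State that rates of grade 1, expected grade 2 and short-term, reversible grade 1-4 hematologic events are not estimated.

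In section 7.2, restrict the request for event characteristics to the events that 7.3 requires, so that all sites submit the same data.

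The cost is wording in two sections and a narrower stated scope for the safety table. No new data are needed, and sites take on no further work.

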## 7.4 Serious Adverse Events

A serious adverse event (SAE) is any adverse event, regardless of causality that:

- Results in death (Grade 5).
- Is life-threatening. Life-threatening means that the person was at immediate risk of death from the reaction as it occurred, i.e., it does not include a reaction which hypothetically might have caused death had it occurred in a more severe form.
- Requires inpatient hospitalization or prolongation of existing hospitalization ≥ 24 hours. Hospitalizations for routine treatment or monitoring not associated with deterioration in condition, elective or pre-planned treatment for a pre-existing condition unrelated to indication under study, and social reasons and respite care in absence of patient's general condition should not be reported as serious adverse events.
- Requires intensive inpatient medical interventions, including mechanical ventilation, pressor support, and/or fluid resuscitation, or emergent surgical operations.
- Results in persistent or significant disability/incapacity. Disability is defined as a substantial disruption of a person's ability to conduct normal life functions.
- Is a congenital anomaly or birth defect.

- Is an important medical event (IME) when, based upon appropriate medical judgment, it may jeopardize the participant and require medical or surgical intervention to prevent one of the outcomes listed above. An example of such a medical event is allergic bronchospasm requiring intensive treatment in an emergency room or in the hospital.
- Any event that is unexpected and related to study drug.

# 7.5 Expedited Reporting

All SAEs must be reported to the Sponsor Investigator immediately, no later than 24 hours of first becoming aware of the event. All SAEs must be reported despite grade or whether or not considered drug related, including those listed in the protocol or investigator brochure and must include an assessment of whether there is a reasonable possibility that the drug caused the event.

The Sponsor Investigator ([name]) and DFCI study team

([contact]) should be informed by email within 24 hours of all SAEs that occur after the patient has provided informed consent, during treatment, or until the participant is taken off study. In the event that the participating investigator does not become aware of the SAE immediately, the participating investigator is to report the event within 24 hours of learning of it and document the time of his or her first awareness of the event.

The study site will have 5 business days from the discovery of the SAE to send a complete expedited report to the Sponsor Investigator.

In addition to SAEs, per DFCI's Expedited Reporting requirements, the following events also require expedited reporting unless they are specifically excluded in Section 7.3:

- Unexpected grade 2 or 3 with a possible, probable, or definite attribution
- Unexpected grade 4 toxicities regardless of attribution
- Dose limiting toxicities that are described in section 5.3

*Pregnancies*: To ensure patient safety, each pregnancy in a patient on study treatment must be reported to the Sponsor Investigator. Pregnancy follow-up should include an assessment of thepossible relationship to the study treatment any pregnancy outcome. Any SAE experienced during pregnancy must be reported. Additionally, pregnancy outcomes should be collected for the female partners of any male study participants. Consent to report information

regarding these pregnancy outcomes should be obtained from the pregnant partner. Sites should follow their institutional policies regarding consenting pregnant partners.

*Unanticipated problems or life-threatening complications:* In the event of an unanticipated problem or life-threatening complications that places subjects or other persons at greater risk of harm than previously recognized occurs, treating investigators must immediately notify the Sponsor-Investigator.

Sponsor-Investigator contact information:

- [name]
- Email: [name]
- [contact]
- DFCI lead study coordinator or study team: [contact]

Outside institutions will report expedited AEs to their respective IRB according to the local IRB's policies and procedures in reporting adverse events. These sites will also complete a DF/HCC AE Reporting form and submit to the Sponsor-Investigator and DFCI study team. The Sponsor-Investigator and DFCI study team will then submit the DF/HCC AE Reporting form from outside institutions to the DFCI OHRS according to DFCI IRB policies and procedures in reporting adverse events.

## 7.6 Reporting to the Food and Drug Administration (FDA)

The Sponsor-Investigator will be responsible for all communications with the FDA. The Sponsor-Investigator will report to the FDA, regardless of the site of occurrence, any serious adverse event that meets the FDA's criteria for expedited reporting following the reporting requirements and timelines set by the FDA. All adverse events reported to the FDA will simultaneously be forwarded to GlycoMimetics, Inc.

Unexpected fatal or life-threatening events associated with the use of the investigational treatment will be reported to the FDA as soon as possible but no later than 7 calendar days after initial receipt of the information.

All other serious unexpected events associated with the use of the investigational treatment will be reported to the FDA as soon as possible but no later than 15 calendar days after initial receipt of the information.

Findings from other clinical, animal, or in-vitro studies that suggest significant human risk will be reported to the FDA as soon as possible but no later than 15 calendar days after initial receipt of the information.

## 7.7 Reporting to GlycoMimetics, Inc.

As the holder of the IND for the Study, DF/HCC Sponsor, [name], MPH, will be responsible for all required regulatory reporting obligations and will submit Adverse Event reports to the FDA in accordance with applicable laws and regulations.

Reports will be submitted to GlycoMimetics, Inc. by the following guidelines:

- Sponsor will send a final copy of all Suspected Unexpected Serious Adverse Reaction (SUSAR) reports to GlycoMimetics, Inc. in parallel to submission to FDA
- Sponsor will send a final copy of all Serious Adverse Event reports to GlycoMimetics, Inc. within 15 days of Sponsor awareness of the event
- All SAE and SUSAR reports should be e-mailed to IQVIA Biotech: [contact].

Any additional information pertaining to the SAE and SUSAR, including complications, progression of the initial event, and recurrent episodes, will be reported as follow up to the original episode.

## 7.8 Reporting to Hospital Risk Management

Participating investigators will report to their local Risk Management office any participant safety reports or sentinel events or unanticipated problems that require reporting according to institutional policy.

## 8. PHARMACEUTICAL INFORMATION

A list of the adverse events and potential risks associated with the investigational or other agents administered in this study can be found in Section 7.1.

# 8.1 Uproleselan Injection

(50 mg/mL)

## 8.1.1 **Description**

Uproleselan is a synthetic, glycomimetic molecule and E-selectin (CD62E) antagonist, with potential anti-thrombotic, antineoplastic and chemo-potentiating activities. Upon administration, uproleselan binds to E-selectin expressed on endothelial cells and prevents their interaction with selectin-E ligand-expressing cancer cells. It has a terminal half-life of approximately 3 hours, and is excreted unchanged in the urine.

Its chemical name is sodium (1R, 3R, 4R, 5S)-3-( $\{2$ -N-acetylamino-2-deoxy-3-O-[(1S)-1-carboxylato-2-cyclohexylethyl]- $\beta$ -D-galactopyranosyl $\}$  oxy)-4-( $\{6$ -deoxy- $\alpha$ -L-galactopyranosyl $\}$ oxy)-5-ethyl-cyclohexan-1-yl-(38-oxo-2,5,8,11,14,17,20,23,26,29, 32,35-dodecaoxa-39-azahentetracontan-41-yl) carboxamide.

Uproleselan is also known as GMI-1271. The molecular formula is C60H108N3NaO27 and the molecular weight is 1326.5.

## 8.1.2 **Form**

Uproleselan will be supplied by GlycoMimetics, Inc. as a ready to use vial (800 mg Uproleselan in 16 ml).

## 8.1.3 Storage and Stability

Uproleselan injection 50 mg/mL is stored per the specified conditions on the label, refrigerated (2°C to 8 °C), prior to administration. Vials of uproleselan will be refrigerated and should be brought to room temperature and gently inverted 4 to 5 times before dose preparation.

Uproleselan is to be kept in a locked and secured storage facility, accessible only to those individuals authorized by the principal investigator (PI).

## 8.1.4 Compatibility

Uproleselan has not been studied for compatibility with other medications, and should be administered in a separate line.

#### 8.1.5 Handling

Qualified personnel, familiar with procedures that minimize undue exposure to themselves and the environment, should undertake the preparation, handling, and safe disposal of uproleselan in a self-contained and protective environment.

#### 8.1.6 Availability

Uproleselan will be provided directly to participating centers by GlycoMimetics, Inc.

## 8.1.7 **Preparation**

Uproleselan must be prepared in one of two ways to maintain stability requirements. Sites should use the practice that best fits within their specific institutional preparation protocol.

1. Uproleselan may be prepared at the time of administration in syringes or IV bags. Only one dose of uproleselan can be prepared when using this method. Allow prepared dose to reach room temperature, and then administer to subject. Storage expiration at controlled room temperature (CRT) is a maximum of 24 hours.

#### OR

2. Uproleselan may be prepared up to 72 hours before administration in syringes or IV bags. Up to two doses of uproleselan may be prepared in advance for each subject (e.g. morning and evening doses). Store prepared doses in refrigerated conditions (+2°C to +8°C). Allow prepared doses to reach room temperature, and then administer to subject.

Dilutions are acceptable for ease of administration, but are not required. Uproleselan may be administered undiluted at a concentration of 50mg/mL or may be further diluted with Sodium Chloride, 0.9% to a final concentration in the range of 5 to 10mg/mL.

Example: If diluting with a 100 mL normal saline (NS) IV bag, remove 36 mL NS from the IV bag. Add the entire contents of uproleselan vial (16 mL) to the remaining 64 ml to reach the final volume of 80 mL/10 mg/mL (concentration). If dilution is performed, the

amount of dilution should be recorded.

Intravenous lines consisting of PVC with DEHP should be avoided when possible. If PVC with DEHP administration sets must be used they should be primed with uproleselan solution no more than 2 hours before dosing. It is highly recommended that uproleselan prepared prior to administration be refrigerated until 1 hour prior to dosing.

